### **Participant Incentives**

Participants will receive \$25 for each completed visit for a total of \$75 during the enrollment period. The monetary incentives will be issued via ClinCard. ClinCard is an electronic debit card method that allows participants to have access to their study incentives immediately at the conclusion of the home assessment. The participant pays

Title: Efficacy of Telemedicine Home Assessments for Identification and Reduction of

Asthma Triggers

PI: [name]

Institution: University of Arkansas for Medical Sciences (UAMS) and Arkansas Children's Hospital/Research Institute (ACH/ACRI)

Sponsor: UAMS Translation Research Institute (UAMS TRI)

no fees to access funds that are securely loaded to their unique debit card. The research staff will assist the participant to create a username and the participant is navigated via [www.myclinocard.com](http://www.myclinocard.com) to select their unique 4-digit PIN. ClinCard is used for in-store and online purchases. It's accepted at ATM locations. The use of ClinCard eases the administrative cost and burden associated with incentive processing. In the event a debit card is lost or damaged, it can be replaced at no cost to the participant. Any existing balance on the previously issued card will automatically transfer to the newly issued debit card. UAMS ClinCard administrator will conduct the research staff ClinCard training prior to study enrollment. The initial debit card will be issued to the parent/adult participant during the consent interview. At the conclusion of each visit, the research staff will load the \$25 incentive onto the debit card.

An alternate incentive payment method will utilize UAMS accounts payable. The research staff will submit the participant incentive via invoice or Workday to UAMS accounts payable. Accounts payable will approve the invoice/requisition and submit a paper check to the participant via the address listed on his/her W9. This process could take upwards of three weeks to process and USPS mail the participant his/her check.

### **Data Handling and Recordkeeping**

The Principal Investigator will carefully monitor study procedures to protect the safety of research subjects, the quality of the data and the integrity of the study. All study participant material will be assigned a unique identifying number. Only study staff will have access to the code and information that identifies the participants in this study. Questionnaires, consent and assent forms will be stored in a binder in a locked protected file in a locked office on ACH campus. Only study personnel will have access to these forms. All participant materials will be recorded in a REDCap database utilizing the unique subject identifier to protect the confidentiality of the individuals. Maintaining a link to identifiers until after data analysis is complete allows for rechecking of data to ensure data integrity and improved study design. For dust samples, only the unique identifying number will be used to identify subject samples during shipping to the processing lab. Samples will be discarded after lab analysis. At the end of the study, documents will be archived according to UAMS/ACH/ACRI policies regarding destruction of research records. Electronic records will be stored on the ACRI/UAMS servers which are password protected.

### **Data Analysis**

#### **Sample size:**

*Analysis for the primary endpoint:* The primary outcome measure is level of dust mite allergens as measured by the MARIA™ test data. Using a one-way analysis of covariance, we estimated that a sample size of 20 in each of the two groups will yield at least 96% power to detect a 4  $\mu\text{g/g}$  difference between group means assuming a common standard deviation of 2 and a two-sided significance level of 5%.

Title: Efficacy of Telemedicine Home Assessments for Identification and Reduction of

Asthma Triggers

PI: [name]

Institution: University of Arkansas for Medical Sciences (UAMS) and Arkansas Children's Hospital/Research Institute (ACH/ACRI)

Sponsor: UAMS Translation Research Institute (UAMS TRI)

**Analysis for the secondary endpoint:** To evaluate the secondary outcome variables, the distribution for each outcome (i.e. home environmental asthma trigger score (heat), ACT score, healthcare utilization, visit satisfaction, and education recall) will be first assessed with summary statistics and graphical measures. It is anticipated that the distribution for some of these variables will be positively skewed. In cases of non-normal data, a logarithmic or square root transformation will be applied to normalize the distribution of the data. Secondary outcomes will be assessed for significant differences between groups and from baseline to 4 months and 6 months using a univariate repeated measure analysis of variance that will include a time x group interaction.

All tests will be two-sided and assume a significance level of 5%. All statistical analyses will be performed using SAS software version 9.4 (SAS Institute Inc., Cary NC, USA).

**Missing data and general considerations:** All reasons for drop out and missing data will be documented and reported. Subjects will be replaced if the dropout rate exceeds the estimate of 10%.

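### The log or square root rule for non-normal secondary outcomes ignores the direction of skew, so it would worsen a left-skewed ACT or satisfaction score

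*Combined protocol and SAP*

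**What the plan says.** The text is in Data Analysis, in the paragraph on the secondary endpoint. It covers five outcomes: the home trigger score (heat), ACT, healthcare utilization, visit satisfaction and education recall. Each distribution "will be first assessed with summary statistics and graphical measures". The plan then says "It is anticipated that the distribution for some of these variables will be positively skewed", and gives the rule: "In cases of non-normal data, a logarithmic or square root transformation will be applied to normalize the distribution of the data". Groups and times (baseline, 4 and 6 months) are then compared "using a univariate repeated measure analysis of variance that will include a time x group interaction", two-sided at 5%.

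The rule sets no condition on the direction of skew. It does not say how to choose between log and square root, or what to do with zeros. No reflected, rank-based, ordinal, count or permutation alternative is named. The check described is on the outcome distributions; model residuals are not mentioned.

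**The concern.** Log and square root are concave: they compress high values and spread out low ones. That helps an outcome with a long right tail. ACT and satisfaction are scores with a top value. If many children score near the top, the tail runs to the left, and the rule then moves the data further from normal, against its stated purpose.

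Three things are at stake:
- **Power.** A stretched low tail inflates the error term of the time-by-group test and lets a few low scores weigh heavily, with only 20 children per arm.
- **Interpretation.** ACT, the symptom measure for Aim 2, would be reported in log or root units instead of points.
- **Feasibility.** Secondary Outcome Measures records exacerbations since the previous contact, and contacts are two months apart. Many children will have none in an interval. The log of zero does not exist and no offset is given, so log can fail even for the outcome most likely to be right-skewed.

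**Working it through.** **1. The plan's own power figure.** The only one is for the primary endpoint: "a sample size of 20 in each of the two groups will yield at least 96% power" (difference 4, SD 2, two-sided 5%). The noncentrality is 4 / (2 × √(2/20)) = 6.32 on 38 degrees of freedom, which gives power above 99.99%. The stated figure is therefore true as a lower bound. It is not an input here; the documents give no power, mean, SD, range or effect for any secondary outcome.

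**2. What the transformations do.** Take an assumed 5–25 score centred at 19, and compare 6 points above (25) with 6 points below (13).

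| Scale | Distance up | Distance down | Down / up |
|---|---|---|---|
| Raw | 25 − 19 = 6 | 19 − 13 = 6 | 1.00 |
| Square root | 5.000 − 4.359 = 0.641 | 4.359 − 3.606 = 0.753 | 1.18 |
| Log | ln(25/19) = 0.274 | ln(19/13) = 0.379 | 1.38 |

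The low side is stretched relative to the high side whatever the distribution, so an existing left skew grows.

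**3. Effect on power.** From the documents: 20 per arm, two-sided 5%, three time points, repeated-measures ANOVA. Assumed: integer scores from beta distributions, joined over time by a Gaussian copula (correlation 0.5 below), with the telemedicine arm's mean raised at 4 and 6 months. The test is F = MS(time × group) / MS(within-subject error), with (3−1)(2−1) = 2 and (40−2)(3−1) = 76 degrees of freedom. There were 1,000 to 2,000 simulated trials per scenario, and all versions were applied to the same data.

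| Assumed score, baseline mean, effect | Skew raw / root / log | Power raw / root / log | Loss root / log (points) |
|---|---|---|---|
| 5–25, mean 19, effect 3 | −0.61 / −0.85 / −1.11 | 70.0 / 65.6 / 60.1% | 4.4 / 10.0 |
| 5–25, mean 20, effect 3 | −0.85 / −1.09 / −1.37 | 64.0 / 58.7 / 53.8% | 5.2 / 10.2 |
| 0–27, mean 20, effect 3 | −0.79 / −1.16 / −1.54 | 45.6 / 40.2 / 35.0% | 5.4 / 10.6 |
| 1–10 (satisfaction-like), mean 8, effect 1 | −0.94 / −1.23 / −1.58 | 38.6 / 35.0 / 30.4% | 3.6 / 8.1 |
| 5–25, no effect | −0.60 / −0.83 / −1.09 | 4.5 / 4.6 / 4.6% | none |

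A wider grid of 24 settings on the 5–25 scale (means 17, 19, 21; effects 1.5 and 3; two spreads; correlations 0.5 and 0.7) gave:
- all settings: loss 0.1 to 5.1 points for square root and 0.4 to 12.1 for log;
- the 10 settings with raw power 30–90% and skew below −0.3: 2.6 to 5.1 and 4.8 to 12.1;
- effect 1.5 with mean 17 or 19 (raw power 12–25%): about 0 to 3.

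**4. Effect shape.** A separate run compared the arms on change between two time points (5–25, mean 20.4, SD 3.8, correlation 0.5, 8,000 trials each). A uniform 1.5-point gain gave 17.5% raw, 16.4% root and 15.2% log. A 6-point gain only in children below 16 gave 10.4%, 11.0% and 11.5%, so the order reversed by about one point.

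**5. Reflection.** In the first row of the table, reflecting the score before transforming gave 83.0% (square root) and 89.6% (log), against 70.0% raw. These figures also depend on the reflection constant.

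**6. Recall.** Table 1 shows no recall measurement at baseline, so no baseline-to-follow-up power figure is given for it.

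**The case against.** The strongest reply is context. The sentence before the rule speaks of positive skew, the distributions are graphed first, and the declared aim is to normalize. A competent analyst who saw left skew would not apply a plain log, and a reflected log is still a logarithmic transformation. This is a fair account of what the authors probably meant. But if the rule is only for right-skewed outcomes, the plan has none for the others and the choice falls to the analyst after seeing the data. Either reading calls for the same edit.

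The second reply is that left skew is nowhere stated. Every child has persistent asthma and an exacerbation in the past year, so ACT need not sit near its ceiling, and two ACT versions are used. This stands, and it makes the power loss conditional.

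Third, leaving scores untransformed is not the most powerful choice if left skew is the premise, since reflected versions did better in several scenarios. This stands too, so a blanket ban on transformation would go too far.

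Fourth, the outcomes are secondary, the trial is a pilot and false-positive risk does not change. This also stands and sets the severity.

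**Conclusion.** The concern holds in conditional form, at minor severity. As written, the rule applies to any non-normal secondary outcome, and for a left-skewed bounded score it does the opposite of what it is for. That follows from the shape of the functions. The problem of zeros in exacerbation counts follows from the visit schedule.

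A reader might infer that the plan will cost ACT, satisfaction and recall some fixed amount of power, of the order of ten points. The documents do not support that: they give no distribution or effect for any of these outcomes. Under the assumed left-skewed scores with 20 per arm, the loss is about 0 to 5 points for square root and 0 to 12 for log. The upper end needs log, marked left skew and a sizeable effect. The loss is near zero for small effects, may reverse slightly if only low scorers improve, and is nil if the scores are not judged non-normal. Type I error stays near 5%. Nothing is claimed about power for recall.

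**What to change.** Replace the transformation sentence in the secondary-endpoint paragraph with:

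*Log or square root transformation will be applied only to right-skewed outcomes, and log only to strictly positive ones. ACT and satisfaction will be analysed on their original point scale; normality will be judged on model residuals, and if these are clearly non-normal the p-value for the same contrast will come from a permutation test.*

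A reflected transformation is an acceptable alternative for left-skewed scores if it is fixed in advance, including its constant. It has the drawback that results leave the point scale.

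Cost: a small change of wording and slightly more analysis work. No new data, visits or participants are needed.

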Institution: University of Arkansas for Medical Sciences (UAMS) and Arkansas Children's Hospital/Research Institute (ACH/ACRI)

Sponsor: UAMS Translation Research Institute (UAMS TRI)

**Study Procedures, Outcome Measures, and Longitudinal Assessments:** For the proposed study, participants will receive home assessments for identification and reduction of asthma triggers via TM or standard of care asthma trigger education. Eligible subjects will undergo a total of 4 visits including an initial, in person screening/enrollment and initial demographic assessment visit, lasting approximately 1-2 hours. After enrollment and randomization, each TM participant will receive three home assessments including an initial baseline home assessment and two follow-up assessments, each 2 months apart (+/- two weeks). The home assessment visits will last approximately 90 minutes. During the TM home assessment, a home environmental asthma trigger assessment checklist (heat) will be utilized to identify potential asthma triggers in the subject's home. TM participants and their household will receive education and supplies, at the time of enrollment, for reduction of any identified triggers as well as education and supplies for general cleaning of the home. The Asthma Home Kit supplies provided to participants will include: Quickie 45TRI automatic sponge mop, child resistant roach and mice bait stations, zippered mattress covers, zippered pillow covers, trash can with lid, trash bags, anti-microbial sponges, rubber gloves, non-toxic all-purpose cleaner, Borax powder, scrubbing pads, Quickie home pro cleaning cloths, broom/dust pan, dusting spray, and paper towels. Each kit will contain labeled instructions on the proper use and/or storage of each item.

For those receiving standard of care education, each subject will receive the same education given to TM subjects for identification and reduction of asthma triggers, but will not receive TM home assessments or trigger reduction kits. Standard of care subjects will be contacted again at 2 months and 4 months (+/- 2 weeks) to assess retention of education materials and to provide additional asthma education and trigger reduction info. All participants will then receive a phone follow-up at 6 months (+/- two weeks) from the time of enrollment.

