### **Outcome Measures:**

Outcomes of patients receiving home assessments/interventions via TM will be compared to patients receiving standard of care trigger education. (**Table 1**) The **primary outcome** will be the mean difference in dust mite levels found in home dust samples at 4 months compared to baseline and between TM and standard of care groups. Other outcomes will be any change in the home environmental asthma trigger assessment score (heat) as a result of trigger mitigation performed at each home visit (TM group), changes in ACT score, comparison in number of exacerbations requiring a healthcare utilization or prescription for systemic steroids, and patient/household family retention of education provided during visits (both groups). We will measure study satisfaction among all participants and telemedicine-specific satisfaction among TM participants.

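### The home trigger score (heat) is assigned a between-group analysis with a 6-month contrast, but it is collected only in the telemedicine arm and only to about 4 months

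*Combined protocol and SAP*

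**What the plan says.** Under Data Analysis, Analysis for the secondary endpoint, the secondary outcome variables are listed as "home environmental asthma trigger score (heat), ACT score, healthcare utilization, visit satisfaction, and education recall". The same paragraph continues: "Secondary outcomes will be assessed for significant differences between groups and from baseline to 4 months and 6 months". The model is a "univariate repeated measure analysis of variance that will include a time x group interaction". No listed outcome is exempted.

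The design sections describe heat differently:

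- Outcome Measures limits it to one arm: "any change in the home environmental asthma trigger assessment score (heat) as a result of trigger mitigation performed at each home visit (TM group"). The same sentence ends with "patient/household family retention of education provided during visits (both groups"), so the text does distinguish outcomes by arm.
- Study Procedures, Outcome Measures, and Longitudinal Assessments ties the score to the TM visit: "During the TM home assessment, a home environmental asthma trigger assessment checklist (heat) will be utilized to identify potential asthma triggers". It fixes the number of visits: "each TM participant will receive three home assessments including an initial baseline home assessment and two follow-up assessments, each 2 months apart". It also says that control subjects do not receive these assessments.
- The Design Overview rules out a formal assessment of control homes.
- The visit content listed under Telemedicine Home Assessment includes an environmental assessment. The parallel list under Standard of Care Asthma Education does not.
- The 6-month contact is a phone call in both arms.
- Table 1 has no row for heat, and Secondary Outcome Measures does not describe it, so neither schedules it for controls or at month 6.

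For recall, Table 1 marks 2, 4 and 6 months but not baseline. On satisfaction, Outcome Measures says: "We will measure study satisfaction among all participants and telemedicine-specific satisfaction among TM participants".

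**The concern.** The analysis section promises results for heat that the design cannot produce: a difference between arms, a difference in change between arms, and a change to 6 months.

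This bears on Specific Aim 1. Hypothesis 1 concerns asthma-related triggers in general, compared with standard education. Of the listed outcomes, only dust mite levels and heat measure triggers. A reader of the analysis section would expect two between-arm trigger results, but there can be only one.

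What heat can give is a before-after change in the TM arm, with no control. It comes from assessments performed by the home visitor, who also delivers the education. If the analysis section is not corrected, an improvement in heat within the TM arm could be read as support for the between-arm hypothesis.

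**Working it through.** The plan gives no figure for heat, so there is none to reproduce. The power statement concerns dust mite levels and does not bear on this point. The check is whether each planned contrast can be estimated from the cells collected.

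**Inputs.** Arms: TM and standard of care (SOC). Times in the stated contrasts: 0, 4 and 6 months (Data Analysis). Heat: TM only, at about 0, 2 and 4 months (Study Procedures; Outcome Measures). Recall: both arms at 2, 4 and 6 months (Table 1; Education Recall).

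**Model.** Let g = 1 for TM and 0 for SOC. The mean at time t is

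E(Y) = μ + αg + τ_t + γ_t g, with τ_0 = γ_0 = 0.

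With times 0, 4 and 6 there are 1 + 1 + 2 + 2 = 6 parameters, so 5 effect degrees of freedom (df): group 1, time 2, interaction 2. With month 2 added there are 1 + 1 + 3 + 3 = 8 parameters and 7 effect df. There is one parameter per arm-by-time cell, so the rank equals the number of filled cells, and the effect df identified equal the rank minus 1.

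**Cells filled**

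| Outcome | Arm | 0 | 2 | 4 | 6 |
|---|---|---|---|---|---|
| Heat | TM | yes | yes | yes | no |
| Heat | SOC | no | no | no | no |
| Recall | TM | no | yes | yes | yes |
| Recall | SOC | no | yes | yes | yes |

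**Effect df identified**

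| Outcome | Times 0, 4, 6 | Times 0, 2, 4, 6 |
|---|---|---|
| Heat | 2 of 6 cells; 2 − 1 = 1 of 5 df | 3 of 8 cells; 3 − 1 = 2 of 7 df |
| Recall | 4 of 6 cells; 4 − 1 = 3 of 5 df | 6 of 8 cells; 6 − 1 = 5 of 7 df |

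**Heat, contrast by contrast.** The observable means are μ + α at month 0, μ + α + τ_2 + γ_2 at month 2, and μ + α + τ_4 + γ_4 at month 4.

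- TM minus SOC at time t is α + γ_t. No SOC mean is observed, so α cannot be separated from μ: 0 of 1 group df.
- Interaction: τ_t and γ_t appear only as a sum. This gives 0 of 2 df, or 0 of 3 with month 2.
- Change from 0 to 6 in TM, τ_6 + γ_6: no month-6 value, so not estimable.
- Changes from 0 to 2 and from 0 to 4 in TM, τ_2 + γ_2 and τ_4 + γ_4: estimable.

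By design, 0 of 40 participants can have heat at all of 0, 4 and 6 months.

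**Recall.** TM minus SOC, α + γ_t, is estimable at 2, 4 and 6 months. Every contrast with month 0 is not.

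**What different collection would change for heat** (8-parameter model)

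| Collection | Rank | Group and interaction | 6-month change |
|---|---|---|---|
| TM only; 0, 2, 4 (as planned) | 3 of 8 | no | no |
| TM only; 0, 2, 4, 6 | 4 of 8 | no | TM only |
| Both arms; 0, 2, 4 | 6 of 8 | to 4 months | no |
| Both arms; 0, 2, 4, 6 | 8 of 8 | yes | yes |

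These are properties of which cells are collected. A larger sample in the same cells would not alter them.

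**The case against.** The strongest reply is that Outcome Measures already restricts heat to the TM group and separates the two satisfaction surveys, so an analyst reading both sections would know which data exist. The listed outcomes also appear in the sentence about inspecting distributions, while the model sentence speaks only of secondary outcomes. Heat is missing from Table 1 and from Secondary Outcome Measures. On this reading the model is a general statement, to be applied where data exist. The error also limits itself: without control data no between-arm estimate for heat can be computed, so no false p-value can result. Finally, Aim 1 rests on dust mites because of the design, and rewording the analysis section does not change that.

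Part of this stands. Nothing here biases the primary outcome or costs power. The satisfaction point is small, because the two surveys are already assigned by arm elsewhere. The reliance on dust mites is indeed a design feature.

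The rest does not rescue the text. The analysis section calls the listed items secondary outcome variables, names heat first, and gives secondary outcomes one analysis without exception. The TM-only tag in Outcome Measures is what contradicts it. The absence of heat from Table 1 only confirms that no other heat data are scheduled. Recall shows that the sentence also fails for a second outcome, whose arm is not in question.

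**Conclusion.** The concern holds and should be corrected. As written, the plan specifies an analysis of heat that the design cannot deliver: no group effect, no interaction and no 6-month change. One of 5 effect df is identified in the stated layout, or 2 of 7 with month 2 included. For recall, only the contrasts with baseline are lost.

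The conclusion assumes that heat is collected as the procedures describe, with no unstated scoring of control homes and no scoring at the 6-month call. The trigger-reduction item in the control visit list specifies no checklist or score. The TM contact offered to all participants for dust sampling is for help with that sampling only.

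The effect is confined to secondary outcomes, and between-arm evidence on triggers rests on dust mite levels alone.

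**What to change.** Revise Analysis for the secondary endpoint so that it agrees with Outcome Measures:

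1. **Heat.** Remove it from the between-group model. Report the TM group's change from baseline to 2 and 4 months with 95% confidence intervals, keeping the stated transformation rule for skewed data. Label it uncontrolled and do not use it as between-arm evidence for Aim 1.
2. **Education recall.** Compare the arms at 2, 4 and 6 months, without a baseline term.
3. **Satisfaction.** Apply the between-group analysis to the outpatient survey given to both arms, and report the telemedicine survey for the TM group only.

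This requires three wording changes and uses data already planned, with no new visit, procedure or participant. The 2-month results for heat and recall go beyond the 4- and 6-month contrasts now named, but the data are already scheduled. The cost is that heat becomes openly descriptive; the between-arm p-value given up was never obtainable.

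If the sponsor does want a between-arm heat comparison, the alternative is to score control homes at 0, 2 and 4 months, and both arms at month 6 if that contrast matters. That adds a procedure and changes the control condition, since those homes are now deliberately left unassessed.

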**Table 1. Summary of Outcome Measures**

	Baseline	2months	4months	6months
Dust Mite Levels	X		X	
Asthma Control Test (ACT)	X	X	X	X
Healthcare Utilization	X	X	X	X
Satisfaction Survey	X	X	X	X
Information Recall Survey		X	X	X

**Primary Outcome Measure:** The primary outcome measure will be the mean difference in dust mite levels found in home dust samples at 4 months compared to baseline and between TM and standard of care groups. Dust mites (*Dermatophagoides farina* and *Dermatophagoides pteronyssinus*) are one of the most common triggers for asthma and are commonly found throughout homes. ELISA testing can be utilized to quantify household dust mite levels with levels  $\geq 2$  mcg/g considered positive. Prolonged reductions in household dust mite concentrations are associated with improved asthma outcomes.

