### **Secondary Outcome Measures:**

**Asthma Control Test (ACT):** The ACT is a validated 5-question ( $\geq 12$  years of age) or 7-question ( $<12$  years of age) survey used to assess asthma control. ACT is used for symptoms monitoring as per guidelines and has been identified as an appropriate asthma control composite score in clinical research.

**Healthcare Utilization:** At baseline, participants will be surveyed to determine the number of acute exacerbations he/she has experienced in the past 12 months resulting in hospitalization, emergency room/sick visits, or systemic steroid use. At each study time point, participants will record acute exacerbations resulting in hospitalization, emergency room or sick visits, or systemic steroid use since the previous asthma education session/TM home assessment visit.

**Visit Satisfaction:** We will administer ACH's outpatient satisfaction survey, supplied by National Research Corporation, at the completion of each visit for both groups. For TM

Title: Efficacy of Telemedicine Home Assessments for Identification and Reduction of

Asthma Triggers

PI: [name]

Institution: University of Arkansas for Medical Sciences (UAMS) and Arkansas Children's Hospital/Research Institute (ACH/ACRI)

Sponsor: UAMS Translation Research Institute (UAMS TRI)

participants, we will administer the telemedicine patient satisfaction survey that will ask respondents to assess four areas regarding the effectiveness and quality of care received via TM: 1) risk and benefits, 2) effectiveness, 3) efficiency, and 4) future adoption.

**Education Recall:** Participants and household parents/caregivers will be administered a questionnaire at each follow-up visit and again via phone call at 6 months to assess recall of education provided during each home assessment.

The ACT, healthcare utilization, visit satisfaction and education recall questionnaires will be completed via a mobile link and take approximately a total of 20 minutes to complete.

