### **Participant Withdrawal**

Since participation is strictly voluntary, participants may withdraw at any time.

Participants will only be replaced if withdrawal occurs prior to the beginning of the first home assessment. Participants may be withdrawn due to non-compliance with study related procedures. Data from the baseline assessment or the subsequent data collection time points for participants who withdraw or who are lost to follow-up will be analyzed.

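### Secondary outcomes: a baseline-adjusted mixed model would give a more precise ACT comparison at almost no cost, and would settle how incomplete participants are kept

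*Combined protocol and SAP*

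**What the plan says.** Under Data Analysis, the paragraph on the secondary endpoint lists the home environmental trigger score, ACT, healthcare utilization, visit satisfaction and education recall. It gives them one method, which compares the two arms and assesses change "from baseline to 4 months and 6 months using a univariate repeated measure analysis of variance that will include a time x group interaction". It names SAS 9.4 but no procedure, covariate, covariance structure or sphericity correction. Analysis of covariance is mentioned only for the primary endpoint.

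The missing-data paragraph says that reasons for dropout will be reported and that subjects will be replaced if dropout exceeds 10%. It gives no analysis method for incomplete participants. The Participant Withdrawal section says that data from baseline or later time points "for participants who withdraw or who are lost to follow-up will be analyzed". It does not say how.

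Table 1 schedules ACT at baseline, 2, 4 and 6 months. Utilization is also collected at 2 months: "At each study time point, participants will record acute exacerbations". Education recall is measured by a "questionnaire at each follow-up visit and again via phone call at 6 months", so it has no baseline. The Outcome Measures section limits the home trigger score to the telemedicine arm.

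**The concern.** When baseline is a response in a repeated-measures ANOVA, the time-by-group interaction compares raw changes from baseline. Under randomization that is valid. It is less precise than adjusting for the baseline score unless baseline and follow-up are almost perfectly correlated. With 40 children, and with ACT bearing directly on Specific Aim 2, the lost precision is worth recovering.

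The second issue is incomplete participants. A wide-format repeated-measures ANOVA needs every named time point and removes a child who misses one. That would not honour the Participant Withdrawal section. It would also rest on a stricter missing-data assumption (missing completely at random) than a likelihood-based model needs (missing at random). Because the plan names no procedure, the analyst could settle this after seeing the data.

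**Working it through.** **The plan's own figure.** The only power statement concerns the primary endpoint: 20 per arm, difference 4, SD 2, two-sided 5%, at least 96%. Those inputs give more than 99.99%, so the statement holds only as a lower bound. Nothing below depends on it. There is no stated figure to reproduce for a secondary outcome.

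**Inputs.** From the documents: 20 per arm, 1:1 allocation, two-sided 5%, and a 10% dropout estimate, so 40 × 0.90 = 36 children or 18 per arm. Assumed, because the documents give no values: a between-group difference of 0.8 SD, equal SD at each visit, and baseline correlation r from 0.3 to 0.9.

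**Variance, in units of SD².** Change from baseline: 2(1 − r). Baseline-adjusted: 1 − r². The ratio of adjusted to change is (1 − r²)/[2(1 − r)] = (1 + r)/2. This is 0.65, 0.75, 0.85 and 0.95 at r = 0.3, 0.5, 0.7 and 0.9, a reduction of 35%, 25%, 15% and 5%.

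**Power for one follow-up visit.** Noncentral t with noncentrality (0.8/√variance) × √(n/2), where n is the number per arm. Degrees of freedom are 2n − 2 for change and 2n − 3 with the covariate. At r = 0.5 and n = 18:
- Change: variance 1, noncentrality 0.8 × 3 = 2.40.
- Adjusted: variance 0.75, noncentrality (0.8/0.866) × 3 = 2.77.

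| r | Change, 36 | Adjusted, 36 | Change, 40 | Adjusted, 40 |
|---|---|---|---|---|
| 0.3 | 50.4% | 68.5% | 54.9% | 73.3% |
| 0.5 | 64.5% | 76.7% | 69.3% | 81.2% |
| 0.7 | 85.3% | 90.3% | 88.9% | 93.2% |
| 0.9 | over 99% | over 99% | over 99% | over 99% |

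With the same 36 children, adjustment alone adds about 18, 12 and 5 points at r = 0.3, 0.5 and 0.7.

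**Keeping partial data.** A 400-run simulation of the planned interaction test used three times, r = 0.5 and 10% lost by 6 months. Power was 69% when incomplete children were dropped and 71% when their available visits were kept. The simulation standard error of each figure is about √(0.7 × 0.3/400) = 2.3 points. This gain is small beside that from adjustment.

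**The 2-month visit.** For the interaction F test at r = 0.5 and 18 per arm, power is 67.8% with three times and 67.3% with four, so nothing is lost by leaving 2 months out. For a baseline-adjusted contrast averaged over follow-up, with 20 per arm, power is 93.6% using 4 and 6 months and 96.8% using 2, 4 and 6.

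**Sphericity.** With an AR(1) correlation of 0.7, simulated type I error of the uncorrected test is about 5.6% to 5.9% for the three named times. This is a minor matter.

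**The case against.** The strongest reply is that this is a pilot with no powered secondary outcome, that raw-change comparison is valid under randomization, and that adjusting for baseline is a choice about efficiency. All of that stands. The point is an improvement, not an error that biases the result.

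A reader might infer that the plan commits to complete cases and so contradicts the Participant Withdrawal section. The documents do not support that. A long-format univariate ANOVA with subject as a factor keeps available visits, and no procedure is named. The conflict arises only if the wide-format version is run. The definite gap is that the plan does not say.

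A reader might also apply a 10% loss to each of three follow-up contacts, arrive at 40 × 0.90³ = 29 completers, and set their change-score power (55%) against adjusted power with all 40 (81%). That does not hold either. The analysis names only two follow-up times, the plan's own dropout figure gives 36, and a mixed model does not recover values never observed. The fair comparison holds the number of children fixed, as in the table.

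Finally, the data on incomplete participants and the 2-month visit add little or nothing to the planned interaction test. That is correct, and the case for change rests mainly on baseline adjustment.

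**Conclusion.** The point holds as a nearly free improvement for ACT. Baseline adjustment lowers the variance of the group comparison by 35%, 25% or 15% at r = 0.3, 0.5 or 0.7. At r = 0.5 and 0.8 SD it is worth about 12 points of power at either sample size. The gain shrinks as r rises and is negligible near 0.9. The effect size and correlations are assumptions. The variance ratio depends only on r and equal SDs.

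Whether incomplete children would be lost cannot be settled from the documents, because it turns on the unnamed procedure. Naming the mixed model removes the doubt, relaxes the missing-data assumption and dispenses with sphericity.

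The adjusted model does not reach every listed outcome. Education recall has no baseline. The home trigger score has no comparison arm. Utilization has a 12-month recall at baseline but is then counted since the previous session, so its baseline is not on the same scale.

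**What to change.** For outcomes with a true baseline on the same scale, chiefly ACT, replace the repeated-measures ANOVA with a mixed model for repeated measures in SAS PROC MIXED:
- REML, unstructured covariance, Kenward-Roger degrees of freedom.
- Responses: the 2-, 4- and 6-month scores.
- Terms: group, visit, group × visit, and the baseline score as covariate.
- Population: every randomised participant with at least one post-baseline value. Children with baseline only cannot enter this model and should be counted and described.
- Report the group difference, with confidence interval, at 4 and 6 months.

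State that the baseline ACT score is the one recorded before randomisation. The protocol places the first home assessment after randomisation and also lists ACT among the items covered at each visit, so the timing should be explicit. Give education recall and the home trigger score their own analyses: a between-arm comparison without a baseline term for recall, and a within-arm change for the trigger score.

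The cost is SAP wording and a different procedure in the software already named. No new data or visits are needed.
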